8.3 Pregnancies

To ensure patient safety, each pregnancy occurring while the patient is on study treatment must be reported to Novartis within 24 hours of learning of its occurrence. The pregnancy should be followed up to determine outcome, including spontaneous or voluntary termination, details of the birth, and the presence or absence of any birth defects, congenital abnormalities, or maternal and/or newborn complications. The follow up period for a newborn of a patient or a partner who becomes pregnant during the study and up to 3 months post last pasireotide LAR dose, is 3months.

Pregnancy should be recorded on a Clinical Trial Pregnancy Form and reported by the investigator to the oncology Novartis Drug Safety and Epidemiology Department (DS&E). Pregnancy follow-up should be recorded on the same form and should include an assessment of the possible relationship to the study treatment any pregnancy outcome. Any SAE experienced during pregnancy must be reported on the SAE Report Form.

Pregnancy outcomes must be collected for the female partners of any males who took study treatment in this study. Consent to report information regarding these pregnancy outcomes should be obtained from the mother.

8.4 Warnings and precautions

No evidence available at the time of the approval of this study protocol indicated that special warnings or precautions were appropriate, other than those noted in the provided Investigator Brochure. Additional safety information collected between IB updates will be communicated in the form of Investigator Notifications. This information will be included in the patient informed consent and should be discussed with the patient during the study as needed.

9 Data collection and management

9.1 Data confidentiality

Information about study subjects will be kept confidential and managed under the applicable laws and regulations. Those regulations require a signed subject authorization informing the subject of the following:

- What protected health information (PHI) will be collected from subjects in this study
- Who will have access to that information and why
- Who will use or disclose that information
- The rights of a research subject to revoke their authorization for use of their PHI.

In the event that a subject revokes authorization to collect or use PHI, the investigator, by regulation, retains the ability to use all information collected prior to the revocation of subject authorization. For subjects that have revoked authorization to collect or use PHI, attempts should be made to obtain permission to collect follow-up safety information (e.g. has the subject experienced any new or worsened AEs) at the end of their scheduled study period.

The data collection system for this study uses built-in security features to encrypt all data for transmission in both directions, preventing unauthorized access to confidential participant information. Access to the system will be controlled by a sequence of individually assigned user identification codes and passwords, made available only to authorized personnel who have completed prerequisite training.

9.2 Site monitoring

Before study initiation, at a site initiation visit or at an investigator's meeting, Novartis personnel (or designated CRO) will review the protocol and eCRFs with the investigators and their staff. During the study, the field monitor will visit the site regularly to check the completeness of patient records, the accuracy of entries on the eCRFs, the adherence to the protocol to Good Clinical Practice, the progress of enrollment, and to ensure that study treatment is being stored, dispensed, and accounted for according to specifications. Key study personnel must be available to assist the field monitor during these visits.

The investigator must maintain source documents for each patient in the study, consisting of case and visit notes (hospital or clinic medical records) containing demographic and medical information, laboratory data, electrocardiograms, and the results of any other tests or assessments. All information recorded on eCRFs must be traceable to source documents in the patient's file. The investigator must also keep the original signed informed consent form (a signed copy is given to the patient).

The investigator must give the monitor access to all relevant source documents to confirm their consistency with the eCRF entries. Novartis monitoring standards require full verification for the presence of informed consent, adherence to the inclusion/exclusion criteria and documentation of SAEs. Additional checks of the consistency of the source data with the eCRFs are performed according to the study-specific monitoring plan.

9.3 Data collection

For studies using Electronic Data Capture (EDC), the designated investigator staff will enter the data required by the protocol into the Electronic Case Report Forms (eCRF). The eCRFs have been built using fully validated secure web-enabled software that conforms to 21 CFR Part 11 requirements, Investigator site staff will not be given access to the EDC system until they have been trained. Automatic validation programs check for data discrepancies in the eCRFs and, allow modification or verification of the entered data by the investigator staff.

The Principal Investigator is responsible for assuring that the data entered into eCRF is complete, accurate, and that entry and updates are performed in a timely manner.

All central labs including pharmacokinetic (PK) and Biomarker (tissue) samples drawn during the course of the study will be collected from the investigator sites and analyzed by Novartis or a central lab contracted by Novartis. The site staff designated by the investigator will enter the information required by the protocol onto the PK and Biomarker sample collection eCRFs, respectively, as well as the designated CRO's requisition form. One copy of the requisition form will be forwarded to the central lab along with the corresponding samples with required information (including study number, patient ID, etc.) and one copy will be retained by the site.

ECG tracings and radiological scans will be transferred to a central reader.

9.4 Database management and quality control

For studies using eCRFs, Novartis personnel (or designated CRO) will review the data entered by investigational staff for completeness and accuracy. Electronic data queries stating the nature of the problem and requesting clarification will be created for discrepancies and missing values and sent to the investigational site via the EDC system. Designated investigator site staff are required to respond promptly to queries and to make any necessary changes to the data.

Concomitant treatments and prior medications entered into the database will be coded using the WHO Drug Reference List, which employs the Anatomical Therapeutic Chemical classification system. Medical history/current medical conditions and adverse events will be coded using the Medical dictionary for regulatory activities (MedDRA) terminology.

Samples and/or data will be processed centrally and the results will be sent electronically to Novartis (or a designated CRO) for the following: biomarkers, PK, central radiology and ECGs.

For EDC studies, after database lock, the investigator will receive a CD-ROM or paper copies of the patient data for archiving at the investigational site.

10 Statistical methods and data analysis

In this study, the results will be reported several times. The first report is planned when the last patient completes 3 months assessment. The result of the primary endpoint will be summarized. On emerging safety concerns observed during the early study period, the second report may be planned when the last patient completes 6 months assessment. The subsequent report is planned when the last available patient completes 12 months assessment. An additional report will be prepared after all patients end study treatment.

10.1 Analysis sets

10.1.1 Full Analysis Set

The Full Analysis Set (FAS) comprises all patients to whom study treatment has been assigned by randomization. According to the intent to treat principle, patients will be analyzed according to the study treatment they have been assigned to during the randomization procedure.

10.1.2 Safety Set

The Safety Set includes all patients who received at least one dose of study treatment. Patients will be analyzed according to the study treatment they actually received.

A precise definition of “actually received” will be added in the RAP.

10.1.3 Per-Protocol Set

The Per-Protocol Set (PPS) consists of a subset of the patients in the FAS without any major protocol deviation and who received at least one dose of study treatment.

Any protocol deviations leading to exclusion from the PPS will be detailed in the validation and planning (VAP) Module 3.

10.1.4 Dose-determining analysis set

Not applicable

10.1.5 Pharmacokinetic analysis set

The pharmacokinetic analysis set (PAS) consists of FAS who have evaluable pharmacokinetic concentration data.

10.2 Patient demographics/other baseline characteristics

Demographic and other baseline data (e.g. age, sex) will be summarized descriptively by study treatment group for the FAS. Categorical data will be presented as frequencies and percentages. For continuous data, mean, standard deviation, median, 25th and 75th percentiles, minimum and maximum will be presented.

10.3 Study treatments (study treatment, concomitant therapies, compliance)

The number of study drug administration will be summarized by dose levels and total-group for Safety set.

Concomitant medications and significant non-drug therapies prior to and after the start of the study treatment will be summarized by dose level study treatment and total-group for the Safety Set.

10.4 Primary objective

The primary objective is to assess the efficacy of pasireotide LAR on the reduction of mean GH levels to $< 2.5\mu\text{g/L}$ and the normalization of IGF-1 at 3 months of study treatment.

10.4.1 Variable

The primary variable is the total-group response rate defined as the proportion of patients with the reduction of mean GH levels to $< 2.5\mu\text{g/L}$ and the normalization of IGF-1 at 3 months of study treatment.

10.4.2 Statistical hypothesis, model, and method of analysis

The total-group response rate at 3 months of study treatment along with the corresponding Clopper-Pearson exact two-sided 90% confidence interval will be provided. The primary analysis will be performed on the FAS.

10.4.3 Handling of missing values/censoring/discontinuations

If the GH and/or IGF-1 samples are taken after 35 days from the date of any LAR injection, the values of GH and/or IGF-1 at the corresponding visit will be treated as missing. In addition, if a patient has less than 3 samples for the assessment of 5-point mean GH levels from the 2-hour profile, the mean GH levels will be considered as missing.

The patients with missing values of mean GH levels and/or IGF-1 at 3 months of study treatment or who discontinue prior to the assessment at 3 months of study treatment will be considered as non-responders.

10.4.4 Supportive analyses

The primary analysis will also be repeated on the PPS.

As subgroup analysis, the primary analysis will also be repeated by prior medication (i.e., somatostatine analogue and dopamine agonist) (yes or no) on the FAS if the number of patients in the subgroup is large enough.

The total-group response rate at 3 months of study treatment along with the corresponding Clopper-Pearson exact 95% confidence interval will be provided on the FAS and PPS.

10.5 Secondary objectives

All secondary efficacy endpoints will be based on the FAS. All secondary endpoints measured up to 3 months of study treatment will be summarized by dose level at randomization study treatment and total-group. All secondary endpoints measured after 3 months of study treatment will be summarized by total-group only.

10.5.1 Key secondary objective(s)

Table 10-1 shows the primary, key secondary and secondary variables for core phase by time point. Table 10-2 shows the secondary variables for extension phase by time point. For the detailed key secondary objectives and secondary objectives, please refer to Table 3-1.

For other key secondary objectives, please refer to Section 10.5.3 (safety and tolerability) and Section 10.5.4 (PK).

Table 10-1 Primary and secondary variables for core phase

| Variables | 3M | 6M | 9M | 12M |
|---|---------------------------------------|-----------------|-----------------|-----------------|
| Proportion of patients with the reduction of mean GH levels to < 2.5µg/L and the normalization of IGF-1 | P (total-group) KS (by dose level) | S (total-group) | S (total-group) | S (total-group) |
| Proportion of patients with the reduction of mean GH levels to < 2.5µg/L | KS (total-group and by dose group) | S (total-group) | S (total-group) | S (total-group) |
| Proportion of patients with the normalization of IGF-1 | KS (total-group and by dose group) | S (total-group) | S (total-group) | S (total-group) |
| Change of tumor volume from baseline | | S | | S |
| Change of mean GH level from baseline | S | | | |
| Symptoms of acromegaly | S | | | |
| Change of PRL level from baseline | S | | | |

P: primary endpoint, KS: key secondary endpoint, S: secondary endpoint

Table 10-2 Primary and secondary variables for core phase

| Variables | 15M | 18M | 21M | 24M |
|---|-----|-----|-----|-----|
| Proportion of patients with the reduction of mean GH levels to < 2.5µg/L and the normalization of IGF-1 | | S | | S |
| Proportion of patients with the reduction of mean GH levels to < 2.5µg/L | | S | | S |
| Proportion of patients with the normalization of IGF-1 | | S | | S |
| Change of mean GH level from baseline | S | | | |

S: secondary endpoint

The response rate at 3 months of study treatment along with the corresponding exact 95% confidence interval will be provided by dose level at randomization study treatment.

For patients with the reduction of mean GH levels to $< 2.5 \mu\text{g/L}$ and patients with the normalization of IGF-1 at 3 months of study treatment, total-group proportions of patients along with the corresponding Clopper-Pearson exact two-sided 95% confidence interval will be provided. The same analyses will be performed by dose level at randomization study treatment.

10.5.2 Other secondary efficacy objectives

10.5.2.1 Other secondary efficacy analyses for core phase

For patients with the reduction of mean GH levels to $< 2.5 \mu\text{g/L}$ and normalization of IGF-1, patients with the reduction of mean GH levels to $< 2.5 \mu\text{g/L}$ and patients with the normalization of IGF-1 at 6, 9 and 12 months of study treatment, total-group proportions along with the corresponding Clopper-Pearson exact two-sided 95% confidence interval will be provided.

Changes of tumor volume at 6 and 12 months of study treatment from baseline will be summarized.

Changes of mean GH level from baseline will be summarized.

Changes of ring size from baseline will be summarized. The shift tables from baseline to the most extreme post-baseline value will also be presented for acromegaly symptoms other than ring size (headache, fatigue, perspiration, paresthesias, and osteoarthralgia).

Changes of PRL level from baseline will be summarized.

10.5.2.2 Other secondary efficacy objectives for extension phase

For patients with the reduction of mean GH levels to $< 2.5 \mu\text{g/L}$ and normalization of IGF-1, patients with the reduction of mean GH levels to $< 2.5 \mu\text{g/L}$ and patients with the normalization of IGF-1 at 18 and 24 months of study treatment, total-group proportions along with the corresponding Clopper-Pearson exact two-sided 95% confidence interval will be provided.

Changes of mean GH level from baseline will be summarized.

10.5.3 Safety objectives

10.5.3.1 Analysis set and grouping for the analyses

For all safety analyses, the safety set will be used. All listings and tables will be presented appropriately.

For each safety variables to be summarized by summary tables, followings will be provided:

1. Summary table by dose level for variables measured up to 3 months of study treatment
2. Summary table for overall patients for variables measured after 3 months of study treatment

For each safety variables to be summarized by shift tables, followings will be provided:

1. Shift table by dose level to compare baseline to the worst value(s) measured up to 3 months of study treatment
2. Shift table for overall patients to compare baseline to the worst value(s) of all post-baseline values

The overall observation period will be divided into three mutually exclusive segments:

1. pre-study treatment period: from day of patient's informed consent to the day before first dose of study medication
2. on-study treatment period: from day of first dose of study medication to 56 days after last dose of study medication
3. post-study treatment period: starting at day 57 after last dose of study medication.

10.5.3.2 Adverse events (AEs)

Summary tables for adverse events (AEs) have to include only AEs that started or worsened during the on-study treatment period, the **study treatment-emergent** AEs. However, all safety data (including those from the pre and post-study treatment periods) will be listed and those collected during the pre-study treatment and post-study treatment period are to be flagged.

The incidence of study treatment-emergent adverse events (new or worsening from baseline) will be summarized by system organ class, preferred term, severity (based on CTCAE grades), type of adverse event and relation to study treatment. Deaths reportable as SAEs and non-fatal serious adverse events will be listed by patient and tabulated by type of adverse event.

Specific safety event categories (SEC) will be considered. Such categories consist of one or more well-defined safety events which are similar in nature and for which there is a specific clinical interest in connection with the study treatment(s).

For each specified SEC, number and percentage of patients with at least one event part of the SEC will be reported.

The incidence of study treatment-emergent adverse events (new or worsening from baseline) occurred in core phase and extension phase will be summarized separately by system organ class, preferred term, severity (based on CTCAE grades), type of adverse event and relation to study treatment.

10.5.3.3 Laboratory abnormalities

For laboratory tests covered by the Common Terminology Criteria for Adverse Events (CTCAE) version 3.0 (see NCI 2006), the study's biometrics and statistical reporting team will grade laboratory data accordingly. For laboratory tests covered by CTCAE, a Grade 0 will be assigned for all non-missing values not graded as 1 or higher. Grade 5 will not be used.

In cases differentials count, the lower limits of normal ranges used in CTCAE definition have to be replaced by a clinical meaningful limit expressed in absolute counts.

For laboratory tests where grades are not defined by CTCAE, results will be graded by the low/normal/high classifications based on laboratory normal ranges.

The following summaries will be generated by dose level or total-group for hematology, biochemistry and urinary laboratory tests:

- frequency table for newly occurring on-study treatment grades 3 or 4
- shift tables using CTCAE grades to compare baseline to the worst on-study treatment value
- for laboratory tests where CTCAE grades are not defined, shift tables using the low/normal/high/low and high classification to compare baseline to the worst on-study treatment value
- listing of all laboratory data with values flagged to show the corresponding CTCAE grades and the classifications relative to the laboratory normal ranges.

10.5.3.4 Other safety data

ECG

- shift table baseline to worst on-study treatment result
- listing of ECG evaluations for all patients with at least one abnormality

Vital signs

Definitions of notably abnormal results have to part of the MAP, CSP and/or RAP.

- shift table baseline to worst on-study treatment result
- listing of vital signs for all patients with at least one notably abnormal result

Gallbladder Ultrasound

Gallbladder data at each visit will be listed.

10.5.3.5 Tolerability

Tolerability will be studied in terms of dose reductions or drug interruption due to an AE.

10.5.4 Pharmacokinetics

PAS will be used in all pharmacokinetic data analysis and summary statistics.

Pharmacokinetic variables

The following PK parameters (Table 10-3) will be determined using non-compartmental method.

Table 10-3 Pharmacokinetic parameters for LAR formulations

| i.m. LAR dose | |
|---------------------------|---|
| $C_{\text{trough day28}}$ | The trough level concentration on day 28 post each injection of LAR, expressed as $C_{\text{trough day28, 1st inj}}$, $C_{\text{trough day28, 2nd inj}}$, $C_{\text{trough day28, 3rd inj}}$ etc. |
| $C_{\text{max,3rd inj}}$ | The maximum concentration post the 3 rd injection of LAR |
| AR | The accumulation ratio calculated as a ratio of [$C_{\text{trough day28,3rd inj}} / C_{\text{trough day28,1st inj}}$] |

Descriptive statistics of pasireotide plasma concentrations will be provided by each time point and dose. Descriptive statistics of PK parameters will be provided by dose. Descriptive statistics will include arithmetic and geometric mean, median, SD, and CV, geometric CV, minimum and maximum. Zero concentrations will not be included in the geometric mean calculation. The concentration data and the PK parameters obtained after dose increase/reduction will be summarized separately.

The effect of patient demographics (e.g. age, body weight, BMI and gender) on PK will be explored, if applicable.

Statistical methods for pharmacokinetic analyses:

The relationship between the dose and the PK parameters ($C_{\text{troughday28,3rd inj}}$) will be explored by the following linear model on the log scale:

$$\ln(\text{PK parameters}) = \text{intercept} + \text{slope} * \ln(\text{Dose}) + \text{error}.$$

In this model, the dose-exposure relationship is mainly characterized by the slope parameter: a value lower/higher than 1 indicates an under/over proportional dose-exposure relationship. The point estimate and associated 90% CI for the slope parameter will be provided for each PK parameters. Point estimates and the corresponding 90% CIs for the PK ratios of 40 mg versus 20 mg and 60 mg versus 20 mg will be presented on the original scale.

10.5.4.1 Data handling principles

Plasma concentrations of pasireotide will be expressed in ng/mL. All concentrations below the limit of quantitation or missing data will be reported as such in the concentration data listings. Concentrations below the limit of quantitation will be treated as zero in summary statistics.

10.5.5 Biomarkers

10.5.5.1 Outline of the data analysis

Not applicable.

10.5.5.2 Data handling principles

Not applicable.

10.5.5.3 Data analysis principles

[figure not shown]
Not applicable.

10.5.6 Resource utilization

Not applicable.

[figure not shown]
10.5.7 Patient-reported outcomes

Not applicable.

10.7 Interim analysis

No interim analysis is planned for this study.

10.8 Sample size calculation

The planned sample size of 30 is determined based on the accuracy of estimated total-group response rate at the end of 3 months.

The response rate is the proportion of responders, where responders are defined as patients with the reduction of mean GH levels to $< 2.5 \mu\text{g/L}$ and normalization of IGF-1. The response rates at 20 mg, 40mg and 60mg in [CSOM230C2110] were comparable (30% at 20mg, 41.7% at 40mg, and 38.5% at 60mg). Furthermore, the dose of pasireotide LAR will be adjusted according to efficacy and safety. It is considered, therefore, that the efficacy of pasireotide LAR can be evaluated more appropriately based on the response rate of all groups combined. In this study, based on the results from CSOM230C2110, the expected total-group response rate will be at least 30%.

In [CSOM230C2305], patients inadequately controlled with 12 month octreotide LAR study treatment were crossed over to pasireotide LAR. The response rate at 3 months after crossover was 17.3% (two-sided 95% CI: [9.8%, 27.3%]). Since a large number of patients who enroll to this study are assumed to be inadequately controlled with octreotide LAR treatment, a clinically meaningful minimum response rate is set as 10% based on the lower limit of two-sided 95% CI, 9.8%.

The expected drop out rate is 10% based on [CSOM230C2305]. The patients with missing values of mean GH levels or IGF-1 at the assessment at 3 months of study treatment or who discontinue prior to the assessment at 3 months of study treatment will be considered as non-responders.

Under these assumptions, the expected total-group response rate adjusted by the expected drop out rate is 27%. The sample size of 30 can demonstrate that the lower limit of the Clopper-Pearson exact two-sided 90% CI for the total-group response rate is not less than the clinically meaningful response rate, 10%.

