| Data analysis | 
Primary endpoint The overall response rate at 3 months of study treatment along with the corresponding exact 90% confidence interval will be provided. The primary analysis will be performed on the FAS.
 
Key Secondary endpoint The response rate at 3 months of study treatment along with the corresponding exact 95% confidence interval will be provided by dose level at randomization study treatment.
 
Sample size calculation The planned sample size of 30 is determined based on the accuracy of estimated overall response rate at the end of 3 months. Under these assumptions, the sample size of 30 can demonstrate that the lower limit of the exact two-sided 90% CI for the overall response rate is not less than the clinically required minimum response rate.
 |
| Key words | Pasireotide, acromegaly, Phase II |

1 Background

1.1 Overview of acromegaly and pituitary gigantism pathogenesis, epidemiology and current treatment

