Preliminary data from the Phase III study [CSOM230C2305] assessed the efficacy and safety of pasireotide LAR vs. octreotide LAR in patients with active medication naïve acromegaly. Patients randomized into 40mg pasireotide LAR and 20mg octreotide LAR. Then dose titration was allowed up and down for efficacy and safety reason, respectively. The primary efficacy variable was the proportion of patients with a reduction of mean GH levels to < 2.5µg/L and the normalization of IGF-1 to within normal limits (age and sex related) at 12 months. A two-sided Cochran-Mantel-Haenszel (CMH) test (adjusting for randomization stratification factor) showed a statistical significant result favoring pasireotide LAR (p-value = 0.005). Odds ratio along with 95% confidence interval was 1.992 (1.222, 3.247), response rates and their corresponding confidence intervals were 31.4% (24.5%, 38.7%) and 19.2%

(13.8%, 25.7%) for pasireotide LAR and octreotide LAR, respectively. The response rate at 3 was same as that at 6 months, it was 30.1%. The most frequent AEs were diarrhoea (38.2% and 45.0%), cholelithiasis (25.8% and 37.2%), headache (18.0% and 26.1%), abdominal pain (17.4% and 22.2%), alopecia (18.0% and 19.4%), hyperglycaemia (28.1% and 8.3%), nausea (12.9% and 21.7%), and nasopharyngitis (15.7% and 15.6%) for pasireotide LAR and octreotide LAR. Among the most frequent AEs (>5%), grade 3 or 4 AEs exceeding 2% were hyperglycaemia (2.8% and 0.6%) and diabetes mellitus (5.6% and 0%).

2 Rationale

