5.2 Inclusion criteria

Patients eligible for inclusion in this study have to meet **all** of the following criteria:

1. Written informed consent obtained prior to any screening procedures
2. Male or female patients of at least 18 years of age
3. Patients with active acromegaly or pituitary gigantism following a or b
 - a. Patients with medication naïve acromegaly or pituitary gigantism demonstrated by:
 - a lack of suppression of GH nadir to <1 $\mu\text{g/L}$ after an oral tolerance test with 75 g of glucose (OGTT) (not applicable for diabetic patients) **or** a mean GH concentration of a 5-point profile within a 2 hour time period of > 5 $\mu\text{g/L}$
 - elevated circulating IGF-1 concentration (age and sex related)
 - Patients who have undergone one or more pituitary surgeries, but have not been treated medically or *de-novo* patients presenting a visible pituitary adenoma on MRI and who refuse pituitary surgery or for whom pituitary surgery is contraindicated

- b. Patients with inadequately controlled acromegaly or pituitary gigantism as defined by a mean GH concentration of a 5- point profile over a 2-hour period $> 2.5 \mu\text{g/L}$ and age and sex related IGF-1 $> 1.3 \times$ upper limit of laboratory normal (ULN), even if acromegaly have been treated for at least 12 weeks with somatostatin analogues or dopamine agonist
4. Patients with a known history or new diagnosis of impaired fasting glucose or diabetes mellitus may be included, however blood glucose and antidiabetic treatment must be monitored closely throughout the trial and adjusted as necessary (see [Section 6.3.3](#))

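### Do the 10% minimum and the 27% expected response rate in the sample size section contradict each other, and does 30 patients promise too much?

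*Protocol*

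**What the plan says.** Protocol section 10.8, repeated in substance in SAP section 7, builds the sample size from two earlier studies.

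- **Expected rate.** "based on the results from CSOM230C2110, the expected total-group response rate will be at least 30" per cent. A 10% drop-out rate, with drop-outs counted as non-responders, follows, and then: "Under these assumptions, the expected total-group response rate adjusted by the expected drop out rate is 27" per cent.
- **Minimum rate.** In the crossover part of CSOM230C2305, in patients uncontrolled after 12 months of octreotide LAR, "The response rate at 3 months after crossover was 17.3" per cent (95% CI 9.8% to 27.3%). The lower limit, rounded to 10%, becomes the minimum because "a large number of patients who enroll to this study are assumed to be inadequately controlled with octreotide LAR treatment".
- **Conclusion.** "The sample size of 30 can demonstrate that the lower limit of the Clopper-Pearson exact two-sided 90% CI" is not below 10%. The protocol summary has the same assurance ("the sample size of 30 can demonstrate that the lower limit of the exact two-sided 90% CI for the overall response rate") without the rate or the 10% figure.

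No power, probability or expected share of uncontrolled patients is given. Protocol section 10.4.2 plans only the total-group response rate with its Clopper-Pearson two-sided 90% interval; it states no hypothesis test or decision rule. The SAP (sections 2 and 5.9.1) records that 33 patients were randomised and that the primary result is in the 12-month report.

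**The concern.** One population assumption appears to be used once and then dropped. It lowers the minimum to 10%, yet it is not visibly applied to the expected rate. Both kinds of patient are eligible under Protocol section 5.2: previously treated patients who are not controlled, and those in this category: "Patients who have undergone one or more pituitary surgeries, but have not been treated medically". For medication-naive patients in CSOM230C2305 the protocol reports: "The response rate at 3 was same as that at 6 months, it was 30.1" per cent. If naive patients respond at 30.1% and the others at 17.3%, the blend drops below 30% once the uncontrolled share passes (30.1 − 30)/(30.1 − 17.3), or about 1%. Seen that way, a rate of at least 30% is not a floor.

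The second worry is the wording of the conclusion. It can be read as an assurance that 30 patients are enough, when on the section's own inputs reaching the minimum is a matter of chance. The 10% figure is also the only benchmark the documents give for reading the primary interval, so a reader could overrate how secure the design was.

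**Working it through.** **Inputs.** n = 30, expected rate 30%, drop-out 10%, minimum 10% and crossover rate 17.3% (Protocol 10.8); dose-group rates 30%, 41.7% and 38.5% (Protocol 10.8) with group sizes 10, 12 and 13 (Protocol 1.2.1.2); n = 33 randomised (SAP 2).

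**1. The plan's own figures.** 0.30 × (1 − 0.10) = 0.27, and 30 × 0.27 = 8.1, so about 8 responders. The Clopper-Pearson 90% lower limit is the 5% quantile of a Beta(x, n − x + 1) distribution. For 8/30 the interval is 14.0% to 43.0%. The lower limit is above 10%, so the statement reproduces at the expected result.

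**2. The count that meets the criterion.**

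| Responders | Lower limit, n = 30 | Lower limit, n = 33 |
|---|---|---|
| 6 | 9.1% | 8.2% |
| 7 | 11.5% | 10.4% |
| 8 | 14.0% | 12.7% |

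At least 7 responders are needed with either number.

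**3. Chance of meeting it.** P(X ≥ 7) for X binomial(n, p):

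| True rate p | n = 30 | n = 33 |
|---|---|---|
| 27% | 73.8% | 82.7% |
| 37.1% × 0.9 = 33.4% | 91.8% | 95.8% |
| 17.3% (every patient uncontrolled) | 25.3% | 34.2% |

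**4. Room in the 30%.** The dose groups give 3/10, 5/12 and 5/13, so 13/35 = 37.1% pooled. If the other patients respond at 37.1% and a share s at 17.3%, the total is 30% when s = (37.14 − 30)/(37.14 − 17.3) = 36%.

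**5. Range over an assumed share.** The documents give no share, so 25%, 50% and 75% are assumptions. The rate is [s × 17.3% + (1 − s) × rest] × d, where d is 0.9 or 1 according to whether drop-out is applied.

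| P(X ≥ 7) | s = 25% | s = 50% | s = 75% |
|---|---|---|---|
| n = 30, rest 30%, d = 0.9 | 61% | 46% | 31% |
| n = 30, rest 37.1%, d = 1 | 89% | 75% | 51% |
| n = 33, rest 30%, d = 0.9 | 72% | 57% | 41% |
| n = 33, rest 37.1%, d = 1 | 94% | 83% | 62% |

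The range is wide because the share, the rate in the remaining patients and the treatment of drop-out in the 17.3% are all unstated.

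**The case for a change.** The strongest case for a change is this. The section relies on a patient mix to justify a low minimum, so it should say what that mix does to the expectation. The SAP treats the mix as relevant, since section 5.9.2.2 reports response by whether patients were uncontrolled on somatostatin analogues. Even at the plan's own 27%, the criterion is missed about one time in four with 30 patients (1 − 0.738 = 0.262). Stating the count of 7 and the probability would cost one sentence.

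Part of this stands: the rationale is incomplete, and the conclusion is not a probability statement. The charge of inconsistency does not stand, for four reasons.

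- A minimum worthwhile rate and an expected rate are different quantities. Taking the first from the lower confidence limit in the hardest-to-treat group and the second from another study is ordinary practice, and both statements can be true.
- The expected 30% is the lowest of the three dose-group rates and sits about 7 percentage points below the pooled 37.1%. That may be an unstated allowance for the mix.
- Protocol section 1.2.1.2 describes the source study as enrolling patients with acromegaly, without limiting it to medication-naive patients. If it included pre-treated patients, blending in 17.3% would count them twice. The 1% calculation depends on replacing the cited source with a different study's rate.
- The section opens by resting the sample size on the accuracy of the estimate, not on power. Read as precision at the expected result, its conclusion is correct.

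**Conclusion.** No change to the plan follows. What remains is a gap in the planning rationale: the documents do not say whether the 30% already allows for octreotide-uncontrolled patients, and they do not translate the precision statement into a probability. That probability is 74% at a true 27% with 30 patients and 83% with the 33 randomised. Other values depend on an uncontrolled share the documents do not give, and run from 31% to 94% over the assumed shares in both sample sizes.

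None of these figures contradicts a stated one, because no power was claimed. The response rate and its exact 90% interval are valid whatever the planning assumptions were. The patient mix is examined where it affects interpretation: by prior medication if numbers allow (Protocol 10.4.4), and by prior somatostatin analogue status (SAP 5.9.2.2). Enrolment is complete and the primary result is reported, so rewording SAP section 7 would alter the record of how the size was chosen without improving any analysis. A report author who wishes to can mention the count of 7 and the 74% and 83% when discussing the result; the plan itself need not.
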